do not dose until 24 to 48 hrs after LP. Follow Visit 2.5

t. Collect drug diary only on this day

Study Visit	1 mg/day										
	Phone Visit	Visit 9	Phone Visit	Visit 10	Phone Visit	Visit 11	Phone Visit	Visit 12	End of Study Drug – Visit 13	Visit 14	End of Study Visit
Study Day	140	168	196	224	252	280	308	336	364	392	546
Study Week	20	24	28	32	36	40	44	48	52	56	78
Medical History	X	X	X	X	X	X	X	X	X	X	X
Concomitant Medications	X	X	X	X	X	X	X	X	X	X	X
Labs (CBC, CMP, TSH)		X		X		X		X	X	X	X
Coagulation panel (PT, PTT, INR)									X ^e		
EKG		X		X		X		X	X	X	X
Vital Signs, Height/Weight		X ^k		X ^k		X ^k		X ^k	X ^k	X ^k	X ^k
Neuro and Physical Exam		X		X		X		X	X	X	X
Cognitive Assessments		X ^{b,c}				X ^{b,c}			X ^{b,c}		X ^{b,c}
Eye exam (OCT)		X							X		X
MRI (preferred) or CT scan											
Randomization											
Volumetric MRI		X ^o							X ^o		X ^o
Blood Biomarkers		X		X		X		X	X	X	X
(Optional) Saliva		X ^r						X ^r	X ^r	X ^r	X ^r
(Optional) Lumbar Puncture ^d									X ^{d,e,r}		
Drug Accountability		X		X		X		X	X		
Adverse Event Assessment	X	X	X	X	X	X	X	X	X	X	X
Dispense Study Drug and Drug Diary		X		X		X		X	X ^t		

a. Screening MMSE, Hachinski, Geriatric Depression Scale (GDS), and CSSR-S

b. ADCOMS (MMSE, ADAS-Cog 13, CDR-SOB)

c. ADCS-ADL

d. All lumbar punctures will be followed by phone call 24-48hrs after lumbar puncture to ensure participant safety

e. Drawn only if opted in for LP. Results required before LP is completed

schedule

f. Dispense of visit drug and first treatment to be completed in clinic

g. If not done within 12 months. Study willing to accept historical CT if done in past 12 months

h. EKG 6 hour post-dose observation. ±10 minutes

i. If participant is of child-bearing potential

k. Height will only be recorded at screening

m. Post-dose vitals every hour ±10 minutes

n. Eye exam (OCT) must be pre-dose

o. vMRI can be done within window of 4 weeks

p. End of study vMRI can be done within window of ±4 weeks

r. Optional substudy procedure if patient opts in

s. If patients opt in for LP on Baseline visit

do not dose until 24 to 48 hrs after LP. Follow Visit 2.5

t. Collect drug diary only on this day

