11. ADVERSE EVENTS AND SERIOUS ADVERSE EVENTS

DEFINITION OF ADVERSE EVENTS (AE)

An adverse event (AE) is any untoward medical occurrence in a clinical study participant administered pharmaceutical (investigational or non-investigational) product. An AE does not necessarily have causal relations with the intervention. An AE can therefore be any unfavorable and unintended sign (including an abnormal finding), symptom, or disease temporally associated with the use of a medicinal (investigational or non-investigational) product. (Definition per International Council on Harmonisation [ICH]).

This includes any occurrence that is new in onset or aggravated in severity or frequency from the baseline condition, or abnormal results of diagnostic procedures, including laboratory test abnormalities. The collections of AEs will begin at the Baseline visit after the first administration of study medication/placebo with the exception of study procedure related AE's that may occur during the screening process.

An unexpected adverse event is any AE, the specificity or severity of which is not consistent with the Investigator's Brochure.

A life-threatening adverse event is any AE that, in the view of the Investigator, places the subject at immediate risk of death from the reaction as it occurred. Disability is defined as a substantial disruption of a person's ability to conduct normal life functions.

DEFINITION OF SERIOUS ADVERSE EVENTS (SAE)

A serious adverse event is any AE that is fatal or life threatening (see below), results in persistent or significant disability (see below) or incapacity, requires inpatient hospitalization or prolongation of an existing hospitalization or is a congenital anomaly/birth defect or results in death. Other important medical events that may not result in death, be life threatening or require hospitalization should also be considered a serious adverse event when, based upon appropriate medical judgment, they may jeopardize the subject and may require medical or surgical intervention to prevent one of the outcomes listed above. Examples of such medical events include allergic bronchospasm requiring intensive treatment in an emergency room or at home, blood dyscrasias or convulsions that do not result in inpatient hospitalization, or the development of drug dependency or drug abuse. Associated with the use of the drug means that there is a reasonable possibility that the experience may have been caused by the drug.

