An Emergency Code Break procedure will be available to the investigator to allow for unblinding of a patient, i.e. informing the investigator to which treatment group the patient has been assigned. Such procedures should only be utilized in emergency situations when the identity of the subject must be known by the investigator in order to provide appropriate medical treatment, i.e. unblinding is not required and should not be performed if knowledge of the patient's treatment group would have no influence on how the patient is being treated in the emergency situation.

EXPECTEDNESS

The Principal Investigator will be responsible for determining whether an adverse event (AE) is expected or unexpected. An AE will be considered unexpected if the nature, severity, or frequency of the event is not consistent with the risk information previously described for the study intervention.

TIME PERIOD AND FREQUENCY FOR EVENT ASSESSMENT AND FOLLOW-UP

The occurrence of an adverse event (AE) or serious adverse event (SAE) may come to the attention of study personnel during study visits and interviews of a study participant presenting for medical care, or upon review by a study monitor.

All AEs including local and systemic reactions not meeting the criteria for SAEs will be captured on the appropriate case report form (CRF). Information to be collected includes event description, time of onset, clinician's assessment of severity, relationship to study product (assessed only by those with the training and authority to make a diagnosis), and time of resolution/stabilization of the event. All AEs occurring while on study must be documented appropriately regardless of relationship. All AEs will be followed to adequate resolution.

Any medical condition that is present at the time that the participant is screened will be considered as baseline and not reported as an AE. However, if the study participant's condition deteriorates at any time during the study, it will be recorded as an AE.

Changes in the severity of an AE will be documented to allow an assessment of the duration of the event at each level of severity to be performed. AEs characterized as intermittent require documentation of onset and duration of each episode.

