Study Coordinator will record all reportable events with start dates occurring after the first administration of study medication/placebo with the exception of study procedure related AE's that may occur during the screening process within 48 hours starting from when site became aware of AE and/or SAE. At each study visit, the investigator will inquire about the occurrence of AE/SAEs since the last visit. Events will be followed for outcome information until resolution or stabilization.

ADVERSE EVENT REPORTING

The condition of each study subject will be monitored throughout the study. Signs and symptoms of possible AEs may be observed by the staff, elicited by asking the patient and/or study partner/informant an open or indirect question (e.g. How have you felt since your last clinic visit?) or volunteered by the subject and/or study partner. All adverse events, whether observed by the investigator or staff, elicited from the subject or study partner, or volunteered by the subject or study partner, will be recorded in the

case report form. Data will include start and end dates, investigator-specified severity and relationship to study drug, and action taken. Whether the event resulted in death, required (or prolonged) hospitalization with persistent or significant disability/incapacity, required intervention to prevent any of the above outcomes, and/or whether it was reported as serious to the medical monitor, DSMB, IRB, and Study Sponsor will also be recorded.

Knowledge of a serious adverse event occurring or worsening in a study subject at any time during the trial must be reported by telephone within 24 hours (if physically possible) to the investigator who will immediately inform the medical monitor, DSMB and IRB in accordance with the IRB's specific requirements. Reports relative to the subject's subsequent course must be submitted to the DSMB until the event has subsided or, in the case of permanent impairment, until the condition stabilizes. At any time following the study, the investigator should immediately notify medical monitor, DSMB, and IRB if he learns of the occurrence of any malignancy or pregnancy involving the participant of a clinical trial, of any serious adverse event that could possibly be related to study drug, or of any congenital anomaly in an offspring of a participant.

SERIOUS ADVERSE EVENT REPORTING

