Statistical analysis of the biomarkers and clinical assessments will be carried out by our biostatistician. Comparisons will assess the change from baseline for the following markers assessed at the frequency indicated in the schedule of visits Table 1):

- vMRI, which is used to estimate the annual rate of brain atrophy.

ANALYSIS OF THE SECONDARY ENDPOINT(S)

Statistical analysis of the biomarkers and clinical assessments will be carried out by our biostatistician. Comparisons will assess the change from baseline for the following markers assessed at the frequency indicated in the schedule of visits Table 1):

- Alzheimer's Disease Assessment Scale - Cognitive (ADAS-Cog13);
- Clinical Dementia Rating-Sum of Boxes (CDR-SOB);
- Mini Mental State Examination (MMSE);
- ADCOMS, which is calculated using components of the three cognitive tests indicated above.

SAFETY ANALYSES

- Concomitant Medications

Concomitant medications will be coded by the World Health Organization (WHO) Drug Dictionary and tabulated by the treatment group.

- Adverse Events

The incidence of all treatment-emergent AEs (TEAEs) and treatment-related AEs will be tabulated by treatment received. These AEs will be classified by system organ class and preferred term using the Medical Dictionary for Regulatory Activities (MedDRA). For incidence reporting, if a subject reported more than one AE that was coded to the same system organ class or preferred term, the subject will be counted only once for that specific system organ class or preferred term. A TEAE is defined as an event that first occurs or worsens in intensity after the administration of study drug. Events recorded between the time the informed consent is signed and the first study drug administration will be listed.

An overview of AEs, which includes subject incidence of TEAEs, treatment-related AEs, SAEs, deaths, and AEs leading to discontinuation, will be presented. For AEs presented by severity, the worst severity during the study will be presented for each subject.

The subject incidence of TEAEs and treatment-related AEs will be summarized by system organ class and preferred term.

- Serious Adverse Events

All SAEs will be listed and summarized in a similar manner to AEs.

- Clinical Laboratory Results

Clinical laboratory values will be measured by a central laboratory.

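### The start of adverse event collection is stated inconsistently, and the narrow rule does not clearly cover the pre-dose baseline lumbar puncture or require a pre-dose severity record

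*Protocol*

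**What the plan says.** **Narrow rule, given twice in Section 11.** The definition of adverse events states: "The collections of AEs will begin at the Baseline visit after the first administration of study medication/placebo". The subsection on time period and frequency tells the coordinator to "record all reportable events with start dates occurring after the first administration of study medication/placebo with the exception of study procedure related" AEs arising in the screening process. That exception is the only one in both places.

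**Wider rule, also in Section 11.** The time-period subsection says "All AEs occurring while on study must be documented appropriately regardless of relationship". The Adverse Event Reporting subsection sends every AE to the case report form, however it came to notice, and makes serious AEs reportable whenever they occur or worsen during the trial.

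**Baseline for AEs.** Section 11 says: "Any medical condition that is present at the time that the participant is screened will be considered as baseline". It adds that if the participant's "condition deteriorates at any time during the study, it will be recorded as an AE".

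**Analysis, Section 12, Safety Analyses.** "A TEAE is defined as an event that first occurs or worsens in intensity after the administration of study drug". Also: "Events recorded between the time the informed consent is signed and the first study drug administration will be listed".

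**Lumbar puncture.** For participants who opt in, Section 1.1 places the first puncture at Visit 2 and moves randomization and first dose to Visit 2.5. Table 1, footnote s, says "do not dose until 24 to 48 hrs after LP".

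**The concern.** Safety is the primary objective, AEs are one of its measures, and tolerability is derived partly from AE frequency. The rule for which events enter the database should therefore have one reading.

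Two groups of events fall between the rules. The first is non-serious harm from an invasive procedure done after eligibility is confirmed but before dosing. The second is any event that begins after screening and before the first dose: it is not baseline, because baseline is fixed at screening, and its start date fails the narrow rule.

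At stake are the completeness of the pre-dose listing and the ability to tell an event that worsened on treatment from one that was already as severe beforehand. Headache matters most here. It is the expected complication of the puncture and also the most frequent reaction in the protocol's own risk table (Section 3.1.1, Table 2: 15% on drug, 14% on placebo).

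**Working it through.** The plan gives no figure to reproduce. The check sets the rules side by side and then gives a rough scale.

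**Step 1. The same event under each rule.** Take a non-serious event, unrelated to any procedure, that starts after consent and before the first dose.
- Narrow rule (AE definition; coordinator instruction): not recorded.
- Wider rule (on-study AEs; Adverse Event Reporting): recorded.
- Section 12 listing: shown if recorded. Under the narrow rule the listing would hold only procedure-related events from screening.

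The two instructions give opposite answers.

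**Step 2. The baseline puncture.** Screening is Visit 1, Day -56 to 0. Visit 2 procedures follow once eligibility is confirmed. The puncture is done at Visit 2, and the first dose follows 24 to 48 hours later at Visit 2.5. Consider a headache that starts in that interval.
- Does it start after the first dose? No.
- Is it procedure-related? Yes.
- Does it fall in the screening process? This cannot be decided, because the term is undefined.

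Visit 2 lists an AE assessment that is not deferred to Visit 2.5, and a phone check follows the puncture. The site will therefore elicit events that the narrow rule may not admit.

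**Step 3. Judging worsening.** A condition present at screening is baseline, and its deterioration is an AE. A condition that begins after screening but before dosing is neither baseline nor, under the narrow rule, a recorded event. If it gets worse after dosing, the AE definition (which includes aggravation) and the treatment-emergent definition both let it count. The narrow rule, however, does not require the pre-dose severity against which worsening would be measured.

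**Step 4. Scale for the puncture.** Section 10 (Optional CSF Collection Sub-Study) gives headache rates below 2% in elderly subjects with atraumatic needles and as high as 10% with standard needles. Opt-in is not given, so 25%, 50% and 100% of 105 are assumed. Headaches = 105 × opt-in × rate.

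| Assumed opt-in | Participants | At 2% | At 10% |
|---|---|---|---|
| 25% | 26.25 | 0.5 | 2.6 |
| 50% | 52.5 | 1.1 | 5.3 |
| 100% | 105 | 2.1 | 10.5 |

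These count all headaches after the baseline puncture. Only those that start before the first dose fall in the gap, so each figure is a ceiling. The Week 52 puncture is unaffected.

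**The case against.** The strongest reply is that this is loose wording which the rest of the protocol repairs.

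**The puncture may count as screening.** It precedes randomization, which moves to Visit 2.5. Section 7 defines screen failures as consented participants who are not later randomized. Visit 2.5 is labelled the first day of dosing, which would put a puncture 24 to 48 hours earlier inside the Day -56 to 0 window. The optional puncture is also described under the screening visit. This reading is reasonable, but Visit 2 carries the same first-day label and comes after eligibility is confirmed. The text supports both readings, and that is the defect.

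**Pre-dose status is largely documented.** Medical history, examination, EKG and vital signs are taken before dosing, and the eligibility check is repeated at Visit 2, so an active infection should exclude the participant unless waived. This stands and limits the harm. These records are not, however, an AE entry with onset and severity.

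**Starting non-procedural AE collection at first dose is legitimate.** This also stands. The fault is that the protocol states that choice and its opposite.

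**Onset time is collected.** Entering a pre-dose headache as a new post-dose event would therefore be a data error rather than something the protocol directs. This stands too.

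**Conclusion.** The inconsistency is real and worth correcting, because it concerns the primary endpoint and a site cannot obey both rules. Followed literally, the narrow rule does not clearly admit non-serious puncture harm before dosing, and it does not require the pre-dose severity of events that begin between screening and first dose.

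The documents do not support four stronger inferences that a reader might draw:
- *Events that worsen on drug are lost.* They are not. Aggravation is in the AE definition, deterioration and severity changes are to be recorded, and Section 12 counts worsening as treatment-emergent. Serious AEs are reportable at any time.
- *The puncture gap contradicts the treatment-emergent definition.* A pre-dose headache that does not worsen is not treatment-emergent. The conflict is with the rule on on-study AEs and with the pre-dose listing.
- *The arms are compared with bias.* The baseline puncture precedes randomization and treatment is blinded, so misclassified headaches would add noise; no bias between arms is shown.
- *A large share of participants is affected.* Assuming 0.5 to 2 events per person-year over a full 56 days, 1 - exp(-rate × 56/365) gives 7.4% to 26.4%, or 8 to 28 of 105. The rates are not in the protocol, 56 days is the maximum wait, and the count covers every pre-dose event rather than those that worsen.

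The size cannot be derived from the documents beyond the ceilings for post-puncture headaches in the working, which depend on opt-in.

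**What to change.** Reconcile the AE passages of Sections 11 and 12:

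1. In the AE definition and the coordinator instruction, make the procedure-related exception run from informed consent to first dose, and name the baseline lumbar puncture.
2. At first dose, record any condition that has arisen since screening, with its onset and current severity. Define baseline for AEs as status before first dose instead of at screening.
3. Align the sentence on documenting on-study AEs with the chosen start point. Section 12 can then separate listed pre-dose events from treatment-emergent ones without change.

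Recording all AEs from consent would also achieve this but is not required. The cost is a few sentences of protocol wording and a few more AE entries. Onset, severity and changes in severity are already collected, and AE assessments already exist at Visits 2 and 2.5.

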The protocol, informed consent form(s), recruitment materials, and all participant materials will be submitted to the Institutional Review Board (IRB) for review and approval. Approval of both the protocol and the consent form must be obtained before any participant is enrolled. Any amendment to the protocol will require review and approval by the IRB before the changes are implemented to the study. In addition, all changes to the consent form will be IRB-approved; a determination will be made regarding whether a new consent needs to be obtained from participants who provided consent, using a previously approved consent form.]

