All SAEs (regardless of suspected causality) should be communicated within 24 hours of discovery of the event to the medical monitor and DSMB members, and to the local IRB within 10 working days.

Any SAEs occurring any time after study participation that are considered by the investigator to be possibly related to study drug must also be reported as outlined above.

The study site will be responsible for notifying the Food and Drug Administration (FDA) of any unexpected fatal or life-threatening suspected adverse reaction as soon as possible, but in no case later than 7 calendar days after the sponsor's initial receipt of the information. In addition, the site must notify FDA and all participating investigators in an Investigational New Drug (IND) safety report of potential serious risks, from clinical trials or any other source, as soon as possible, but in no case later than 15 calendar days after the sponsor determines that the information qualifies for reporting.

REPORTING EVENTS TO PARTICIPANTS

Participants will be informed to discontinue the study drug if blood or cardiac toxicity is discovered. The hematologic values indicative of severe AEs are those listed in exclusion criteria. Refer to section, Procedure Used in Case of Toxicity.

EVENTS OF SPECIAL INTEREST

Occurrences of acute overdose should be reported for tracking purposes. In this study, an overdose is defined as a dose greater than the specified dose and requires medical attention.

REPORTING OF PREGNANCY

Because Siponimod is a suspected teratogenic agent based on animal studies, females must be surgically sterile (bilateral tubal ligation, oophorectomy, or hysterectomy) or of non-childbearing potential.

Although it is currently unknown whether Siponimod present in semen can affect the growth of fetuses, male participants will be asked to use contraceptive methods preventing the exposure of fetuses to semen.

If, despite the use of contraceptives as described in this protocol, the partner of a subject becomes pregnant during the study, she will be followed through the end of her pregnancy. A Pregnancy Notification/Outcome Consent Form and Pregnancy Notification Form will be completed and faxed to the Drug Safety Department at Research Pharmaceutical Services Inc. (RPS). The outcome of the pregnancy and the medical condition of any resultant offspring will be reported on a Pregnancy Outcome Form.

UNANTICIPATED PROBLEMS

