The Office for Human Research Protections (OHRP) considers unanticipated problems involving risks to participants or others to include, in general, any incident, experience, or outcome that meets **all** of the following criteria:

- Unexpected in terms of nature, severity, or frequency given (a) the research procedures that are described in the protocol-related documents, such as the Institutional Review Board (IRB)-approved research protocol and informed consent document; and (b) the characteristics of the participant population being studied.
- Related or possibly related to participation in the research (“possibly related” means there is a reasonable possibility that the incident, experience, or outcome may have been caused by the procedures involved in the research); and
- Suggests that the research places participants or others at a greater risk of harm (including physical, psychological, economic, or social harm) than was previously known or recognized.

UNANTICIPATED PROBLEM REPORTING

The investigator will report unanticipated problems (UPs) to the reviewing Institutional Review Board (IRB), NIH, the NI and to the DSMB. The UP report will include the following information:

- Protocol identifying information: protocol title and number, PI’s name, and the IRB project number.
- A detailed description of the event, incident, experience, or outcome.
- An explanation of the basis for determining that the event, incident, experience, or outcome represents an UP.
- A description of any changes to the protocol or other corrective actions that have been taken or are proposed in response to the UP.

To satisfy the requirement for prompt reporting, UPs will be reported using the following timeline:

- A Major Protocol Deviation – a deviation, based on the clinical judgment of the PI or their designee, determined to significantly impact the scientific soundness of the research plan or suggest the research placed participants or others at a greater risk of harm (physical, psychological, economic, or social harm) not previously recognized. A major deviation meets all criteria for an UP involving risk. Major Protocol Deviations /UPs will be reported to local IRB within 10 days of investigator becoming aware. These will be reported to the DSMB and to the study sponsor within 24h of the investigator becoming aware of the event.

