- Any other UP will be reported to the DSMB and to the study sponsor within 5 days of the investigator becoming aware of the problem. These UPs will be reported to the site’s Institute QA Monitor within 7 days, and to the local IRB at continuing renewal.

REPORTING UNANTICIPATED PROBLEMS TO PARTICIPANTS

The study site will report UPs to participants who are directly involved in the UP, or if the UP identifies risks that may impact their willingness to participate. Appropriate actions for the continuation or withdrawal from the study will be discussed with the involved participants.

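### Unanticipated problems other than major protocol deviations have no prompt route to the local IRB in the protocol's own reporting timeline, and for serious events that timeline conflicts with the SAE rules

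*Protocol*

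**What the plan says.** Section 11, Unanticipated Problems, requires a UP to meet all of three criteria: it is unexpected, it is related or possibly related to the research, and it "Suggests that the research places participants or others at a greater risk of harm" than was previously known.

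Unanticipated Problem Reporting then opens its schedule with "To satisfy the requirement for prompt reporting, UPs will be reported using the following timeline". The schedule has two branches:

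- **Major protocol deviations.** "Major Protocol Deviations /UPs will be reported to local IRB within 10 days of investigator becoming aware". The DSMB and sponsor are told within 24 hours. A deviation is major if it significantly affects the scientific soundness of the research plan or suggests greater risk of harm. The text adds that a major deviation meets every UP criterion.
- **Everything else.** "Any other UP will be reported to the DSMB and to the study sponsor within 5 days" of awareness, then to the site's "Institute QA Monitor within 7 days, and to the local IRB at continuing renewal".

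Other parts of the protocol also bear on what the IRB hears:

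- Section 11, Adverse Event Reporting: the investigator informs the IRB of an SAE immediately, following the IRB's own requirements.
- Section 11, Serious Adverse Event Reporting: all SAEs, whatever the suspected cause, go to the medical monitor and DSMB within 24 hours "and to the local IRB within 10 working days".
- Section 10, Safety Monitoring: IRB notification of adverse events follows institutional policy, with no interval stated.
- Statement of Compliance: "Any amendment to the protocol will require review and approval by the IRB before the changes are implemented to the study", and consent form changes also need IRB approval.

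**The concern.** Continuing renewal is a calendar event that has nothing to do with when a problem arises. A report tied to it is prompt only by chance, so the second branch fails the purpose that the section sets for itself.

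The order of priority is also odd. A deviation that affects only scientific soundness, with no suggestion of harm, reaches the IRB in 10 days. A newly recognised risk from the drug, the product or a procedure must suggest harm to be a UP at all, yet it has no prompt date. Of the recipients named for these UPs, only the IRB, which must approve protocol and consent changes, has no fixed number of days.

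This matters more than usual here. Safety and tolerability are the primary objective. Section 3 says little is known about adverse events of this drug outside multiple sclerosis, and Section 6 (Justification for Dose) finds no literature on its cardiac effects above age 60. New risk information is what the trial is meant to produce.

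**Working it through.** The document states no figure to reproduce. The check is to set the routes to the local IRB side by side and see which kinds of UP each one covers.

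| Type of event | Route in the protocol | Time to local IRB |
|---|---|---|
| Major protocol deviation | Section 11, Unanticipated Problem Reporting | 10 days |
| SAE | Section 11, Adverse Event Reporting | immediately, per IRB requirements |
| SAE | Section 11, Serious Adverse Event Reporting | 10 working days |
| Any adverse event | Section 10, Safety Monitoring | institutional policy, no interval given |
| Any other UP | Section 11, Unanticipated Problem Reporting | at continuing renewal |

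**Step 1: UPs that are also SAEs.** Three rules apply to the same event: immediately, 10 working days, and continuing renewal. They cannot all govern, and the text does not say which one does. In practice an SAE rule would probably be followed, so the defect here is a conflict rather than a gap.

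**Step 2: UPs that are non-serious adverse events.** The SAE rules do not apply. An example is a non-serious reaction occurring at an unexpected frequency, since the UP definition counts unexpected frequency as well as nature and severity. The only possible shorter route is the institutional policy, whose timing is not given.

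**Step 3: UPs that are not adverse events.** The definition includes psychological, economic and social harm. A confidentiality breach is an example: Section 8 puts subject name and date of birth on the bottle labels. A product or labelling fault is another: Section 10, Complaint Handling, sends product complaints to the medical monitor and names no IRB step. Neither the SAE rules nor the adverse event policy clause covers such events, so the renewal rule stands alone.

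**Step 4: size of the delay.** The renewal interval is not in the document. Assume 6 to 12 months. A UP that arises just after a renewal then waits up to:

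- 6 months: 52 / 2 = 26 weeks = 26 × 7 = 182 days, or 182 / 10 = about 18 times the 10-day interval for a major deviation.
- 12 months: 52 weeks = 52 × 7 = 364 days, or 364 / 10 = about 36 times that interval, and as long as the 52-week dosing period.

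These are upper limits under the assumption. A UP that arises just before a renewal would wait very little.

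**Step 5: the equivalence sentence.** Being major requires either an effect on scientific soundness or a suggestion of harm. Being a UP requires all three criteria, including greater risk. A deviation can therefore be major through the first alternative without being a UP, and the statement that a major deviation meets every UP criterion does not follow from the section's own definitions.

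**The case against.** The strongest reply is that oversight is faster than the renewal clause suggests. The DSMB and sponsor know of every such UP within 5 days and the QA monitor within 7. Section 10 has moderate to severe adverse events reported immediately to the medical monitor and DSMB. The SAE definition takes in other important medical events, so a cardiac event that needs intervention would normally reach the IRB by an SAE route. The institutional policy may also cover non-serious adverse events. All of this stands, and it narrows the gap to non-serious UPs and UPs that are not adverse events. It does not remove it: no passage gives those UPs a fixed prompt date with the IRB.

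It might also be said that the slash in the 10-day sentence, "UPs will be reported to local IRB within 10 days of investigator becoming aware", brings all UPs under that interval. The next branch, which is expressly for any other UP, rules that reading out.

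A reader might infer that consent and protocol changes cannot be made in time, and might multiply accrual by the delay to count subjects consented under an outdated form. The documents do not support this. The Statement of Compliance requires approval before a change is implemented. It does not restrict when an amendment may be submitted, and submitting one would itself inform the IRB. Section 11 also has the site tell participants who are directly involved in a UP or whose willingness to take part may be affected. What remains true is that nothing requires an early submission, so when the IRB learns of such a UP is left to discretion.

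**Conclusion.** The point holds in limited form. The protocol sets a rule that contradicts its own stated purpose of prompt reporting. This is wrong text, not detail left to another document. For UPs that are also SAEs, the protocol gives three inconsistent timings. For non-serious UPs and those that are not adverse events, it gives no prompt IRB route.

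The possible wait of about 26 to 52 weeks, against 10 days for a major deviation, rests wholly on an assumed renewal interval of 6 to 12 months. A flat statement that the delay is a year would go beyond the document, as would a statement that every UP waits for renewal. The defect concerns participant protection and has no bearing on sample size or analysis. It should be corrected, although the SAE and DSMB routes mitigate it in part.

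**What to change.** 1. In Section 11, Unanticipated Problem Reporting, change the clause "Institute QA Monitor within 7 days, and to the local IRB at continuing renewal" so that the IRB part gives the interval the section already uses for major deviations: 10 days from the investigator becoming aware. The 7-day report to the QA monitor can stay.
2. State that when a UP is also an SAE, the SAE route governs. Reconcile the two SAE timings for the IRB (immediately in Adverse Event Reporting, 10 working days in Serious Adverse Event Reporting) so that there is one rule.
3. Replace the sentence that equates every major deviation with a UP by one saying that a major deviation is also a UP only when it meets all three UP criteria. Naming the harm criterion alone would not be enough, because it would drop the requirements that the event be unexpected and related or possibly related.

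The cost is a few sentences in an amendment and a small number of additional prompt reports at a single site. Sample size, endpoints and analysis are unaffected.
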